PH1 is primarily a pediatric disease, with symptoms first appearing in approximately half (48.6%) of the patients in the Rare Kidney Stone Consortium Primary Hyperoxaluria Registry between birth and four years of age. Approximately three-quarters of patients (74.7%) showed signs or symptoms before the age of 15 and 83.5% showed symptoms before 20 years of age. In comparison, only 16.5% of patients first displayed symptoms after age 20. Additionally, nearly one third (29.9%) of patients were diagnosed between birth and four years of age and two-thirds (66%) were diagnosed before 20 years of age.[Atlas 2007] The majority of patients are, therefore, diagnosed as children, and consequently, are more likely to have some preservation of renal function at time of diagnosis.

Most PH1 patients exhibit urinary oxalate excretion greater than 2-fold the upper limit of normal (ULN), although patients with severely compromised renal function may have lower excretion rates. PH1 is definitively diagnosed by gene sequencing to detect pathological mutations in *AGXT*, or by evaluation of AGT enzymatic activity in liver tissue obtained by biopsy.

Currently, there are no approved therapies for the treatment of PH1. Disease management is based on supportive measures, including high fluid intake, potassium citrate (to increase urinary oxalate solubility), vitamin B6, and treatment of complications such as urinary tract stones and

infections. Dietary modification plays a minor role in treatment since endogenous oxalate production far exceeds dietary intake. Patients progressing to or presenting with end-stage renal disease (ESRD) require intense kidney dialysis. However, dialysis, day and night, 6 days per week, may be inadequate to effectively offload accumulating oxalate.[Cochat 2012] Combined liver/kidney transplantation offers potentially curative therapy, but with limited availability, the attendant medical risks, and intense use of health care resources. Therefore, there is a high unmet medical need for additional treatments for patients with PH1. The deterioration of renal function that occurs in PH1 disease indicates the importance of investigating potentially disease-modifying interventions as early as possible after diagnosis.

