4. PATIENT POPULATION

4.1. Patient Definitions

The populations (analysis sets) are defined as follows:

- Safety Analysis Set: All patients who receive any amount of study drug.
- PD Analysis Set: All patients who receive any amount of study drug and who have at least 1 post-dose urine sample for PD.
- PK Analysis Set: All patients who receive any amount of study drug and who have at least 1 post-dose PK concentration measurement.

The Safety Analysis Set will be used to analyze safety and clinical activity data. The PK and PD Analysis Sets will be used to conduct PK and PD analyses, respectively.

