5. GENERAL STATISTICAL METHODS

5.1. General Methods

Continuous data will be described using descriptive statistics such as the number of observations (n), mean, standard deviation, standard error, median, quartiles, minimum, and maximum. For the summary statistics of all numerical variables unless otherwise specified, minimum and maximum will be displayed to the same level of precision as reported. Median and mean will be presented to the level of precision collected in the database plus 1 additional decimal. The standard deviation and standard error will be presented to the level of precision collected in the database plus 2 additional decimals.

For assessments with repeated collections at a given study visit (e.g., ECG parameters, height for patients <18 years of age), the mean will represent the value at the visit for all parameters except for 24-hour urine PD parameters. For 24-hour urine PD parameters, if there are repeated collections at a particular visit then the median will represent the value at that visit. For biomarker and/or laboratory data, if any value is recorded as less than the lower limit of quantification (LLOQ) then the value used for calculations will be assigned a value of LLOQ.

Categorical and ordinal data will be described using the patient count and percentages in each category. When count data are presented, the percentage will not be presented when the count is zero.

Study Day 1 will be defined as the day of the first dose of lumasiran in this study. Study day will be calculated relative to the first dose date of study drug for all patients:

If the assessment date is after the date of first study drug dose, then the study day will be calculated as:

$$\text{Study Day} = \text{Date of assessment} - \text{date of first dose of study drug} + 1,$$

If the assessment date is before the date of the first dose of study drug, then the study day will be calculated as:

$$\text{Study Day} = \text{Date of assessment} - \text{date of first dose of study drug}$$

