5.4. Dose Groups

All tables and figures will be presented by the initial dose regimens in this study, unless otherwise specified:

- 1 mg/kg once monthly
- 3 mg/kg once every 3 months
- Pooling of 1 mg/kg once monthly or 3 mg/kg once every 3 months
- 3 mg/kg once monthly
- Total

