7.2. Secondary Endpoints

7.2.1. Evaluate the pharmacodynamic effect of lumasiran on urinary oxalate excretion

The analysis of 24-hour urinary oxalate excretion corrected for BSA will be based upon the results that meet the validity criteria (i.e., creatinine excretion ≥ 10 mg/kg, duration of collection 18 to 26 hours, no missing voids and the sample was not collected within 14 days after the most recent dialysis session, if applicable). The analysis will be generated separately based upon data from laboratories using a clinical diagnostic PD assay or quantitative PD assay.

Correlations between the assays will be performed comparing oxalate values, 24-hour urinary oxalate corrected for BSA, change and percentage change of 24-hour urinary oxalate corrected for BSA. Per-patient spaghetti plots may also be generated to compare the results over time.

24-hour urinary oxalate (mmol/24h/1.73m²) corrected for BSA at each visit per patient is calculated as follows:

$$[\text{Urine oxalate concentration (umol/L)/1000 (umol/mmol)}] * [\text{24hr urine volume (mL)/1000 (mL/L)}] * [\text{24 hours/actual collection hours}] * 1.73 / (\text{BSA})$$

where BSA=square root (mean height (cm)*weight (kg)/3600) at the visit.

Data will be summarized descriptively at baseline and at each post-baseline visit. Tabular summaries will include actual value, change from baseline and percent change from baseline at each scheduled visit. Per-patient figures and mean (+/-SEM) plots over time of the actual values, change from baseline and percent change from baseline will be generated. A table of the maximum percent reduction per patient will also be generated.

An analysis of the percentage of time at or below 1.5 x ULN will also be summarized. For each patient, the percentage of time will be calculated as follows:

$$\text{Percentage of time at or below 1.5x ULN} = \frac{\text{cumulative months at or below 1.5 x ULN}}{\text{cumulative months of valid assessments}} * 100$$

where cumulative months at or below 1.5x ULN will be defined as the summation across all intervals that met the threshold of at or below 1.5x ULN and cumulative months of valid assessments will be defined as the summation across all valid post-baseline collections. In order to quantify the months at or below 1.5x ULN, a linear interpolation method will be used to determine the bookend dates at which the patient crossed into the threshold and crossed out of the threshold.

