Descriptive statistics of percentage of time at or below 1.5x ULN (among the subset of patients who had at least 1 post-baseline value that was at or below 1.5x ULN) will be presented. In addition, the number of patients and associated percentage of patients in each category (e.g., <25%, 25 to <50%, 50 to <75%, and $\geq 75\%$) will also be presented.

The analysis of the percentage of time will also be calculated using the threshold of at or below ULN.

7.2.2. Change in estimated glomerular filtration rate (eGFR) and measured creatinine clearance over time

Analyses of eGFR and measured creatinine clearance over time will be performed on the Safety Analysis Set.

The eGFR (mL/min/1.73m²) will be calculated from serum creatinine (SCr) based on the Modification of Diet in Renal Disease (MDRD) formula for patients ≥ 18 years of age at enrollment and the Schwartz Bedside Formula for subjects <18 years of age at enrollment in the parent study.

MDRD Formula

- $\text{eGFR (mL/min/1.73m}^2\text{)} = 175 \times (\text{SCr } [\mu\text{mol/dL}] / 88.4)^{-1.154} \times (\text{age})^{-0.203} \times (0.742, \text{ if female}),$
or $\times (1.212, \text{ if African American})$

Schwartz Bedside Formula

- $eGFR (\text{mL/min}/1.73\text{m}^2) = (36.2 \times \text{height [cm]}) / \text{Scr} (\mu\text{mol /dL})$

The eGFR ($\text{mL/min}/1.73 \text{ m}^2$) will be categorized into the following categories: ≥ 90 , 60 to < 90 , 30 to < 60 , 15 to < 30 , and < 15 . A shift table of baseline to worst post-baseline eGFR (i.e., category with the lowest value) will be presented. Additionally, the eGFR will also be summarized descriptively at each scheduled visit. The descriptive statistics will include actual value, change from baseline and percent change from baseline at each scheduled visit. Per-patient plots and mean ($+\text{- SEM}$) plots over time of the actual values, change from baseline and percent change from baseline will be generated. Additionally, slope of change of eGFR over time is will be estimated by a linear mixed effect model, if appropriate.

Analysis of measured creatinine clearance will be performed on the PD Analysis Set. The analysis will include only valid values (note: valid is defined as: creatinine $\geq 10 \text{ mg/kg}$, duration of collection 18 to 26 hours, no missing voids, and the sample was not collected within 14 days after the most recent dialysis session, if applicable).

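### Percentage of time at or below 1.5x ULN is summarised only in patients who reached it at least once, so the printed mean overstates time at target by a factor of 1/p (p = share ever at target)

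*SAP*

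**What the plan says.** SAP 7.2.1 adds a time-at-threshold analysis to the by-visit summaries of urinary oxalate. The measure is individual: "For each patient, the percentage of time will be calculated as follows", as months at or below 1.5x ULN divided by months of valid post-baseline assessment, with crossing dates found by linear interpolation. The denominator does not depend on whether the patient ever reached the threshold.

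The descriptive statistics are then limited to patients "among the subset of patients who had at least 1 post-baseline value that was at or below 1.5x ULN". No all-patient version is specified.

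Three further provisions bear on the output:

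- The same section tabulates "the number of patients and associated percentage of patients in each category" (four bands, from below 25% to 75% or more), without a denominator.
- It adds: "The analysis of the percentage of time will also be calculated using the threshold of at or below ULN". The population for that repeat is not restated.
- SAP 5.4 says: "All tables and figures will be presented by the initial dose regimens in this study", unless otherwise specified. SAP 5.1 lists the statistics as n, "mean, standard deviation, standard error, median, quartiles, minimum, and maximum".

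The natural full population is the PD Analysis Set in SAP 4.1: "All patients who receive any amount of study drug and who have at least 1 post-dose urine sample for PD".

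**The concern.** Patients enter the summary according to the outcome it measures. Those left out have the worst possible result, so the mean can only move in the favourable direction. These tables are the plan's only summaries of how long patients stay at target, and a reader will tend to take the figure as describing treated patients in general.

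Four things are at stake:

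- **Mean, median and quartiles.** The mean can be rescaled if the evaluable N is printed beside n. The median and quartiles cannot.
- **Two thresholds.** No patient can spend more time at or below ULN than at or below 1.5x ULN. If the subset is redefined at ULN, which is the natural reading, the two means describe different patients and the stricter one can print higher.
- **Category table.** Never-reachers may be counted in the lowest band or left out. Two programmers could produce different percentages from the same text.
- **Small columns.** With at most 20 patients split by initial regimen, one never-reacher can change the apparent order of columns. No regimen comparison of oxalate is planned, so the risk is misreading and not a wrong test.

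**Working it through.** The plan states no expected percentage of time and no value of p, so there is no figure to reproduce.

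**Inputs.** Up to 20 patients (Protocol 4.3); the subset rule and interpolation (SAP 7.2.1); regimen columns (SAP 5.4). Assumed: p, the oxalate distribution on treatment, and about 7 patients per regimen (20 over 3).

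**Step 1: the identity.** A line joining two values above the threshold stays above it, so an evaluable never-reacher scores exactly 0%. Hence

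mean(all) = p x mean(reachers) + (1 - p) x 0, and mean(reachers) / mean(all) = 1/p.

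| Ever at target | Factor 1/p | A printed 70% means, in all patients |
|---|---|---|
| 20/20 | 1.00 | 70% |
| 19/20 | 1.05 | 66.5% |
| 16/20 | 1.25 | 56% |
| 10/20 | 2.00 | 35% |

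In a column of 7 the factor is 7/6 = 1.17 at 6/7 and 7/5 = 1.40 at 5/7.

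**Step 2: simulation of the SAP rule.** Assumed model: log-normal oxalate/ULN, within-patient log-SD 0.2, and 11 visits (months 3, 6, 9, 12, then every 6 months to 54). Population medians were 1.2, 1.5 and 1.8x ULN. Every simulated never-reacher scored 0%. Entries are in that order of medians and hold to within about 1 percentage point.

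| Threshold | Between-patient log-SD | p | SAP mean (%) | All-patient mean (%) |
|---|---|---|---|---|
| 1.5x ULN | 0 | 1.00 / 1.00 / 0.89 | same / same / 13.6 | same / same / 12.1 |
| 1.5x ULN | 0.2 | 0.99 / 0.92 / 0.72 | 81 / 53 / 32 | 80 / 49 / 23 |
| 1.5x ULN | 0.4 | 0.90 / 0.78 / 0.63 | 77 / 64 / 53 | 69 / 49 / 33 |
| ULN (subset redefined) | 0.4 | 0.63 / 0.42 / 0.26 | 53 / 41 / 33 | 33 / 17 / 8 |

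At log-SD 0.4 and population median 1.8, the median percentage of time at or below 1.5x ULN is about 52% in the SAP subset and about 10% in all patients.

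**Step 3: the two thresholds, if the subset is redefined at ULN.** Suppose 5 of 20 patients have 100% at 1.5x ULN and 90% at ULN, and 15 have 40% and 0%. At 1.5x ULN all 20 qualify: (5 x 100 + 15 x 40)/20 = 55%. At ULN only 5 qualify, so the table prints 90%; the all-patient mean is 5 x 90/20 = 22.5%. In the simulation this inversion occurs in 3-13% of 20-patient and 13-17% of 7-patient replicates at log-SD 0.4, in at most about 3% at log-SD 0.2, and not at all at log-SD 0.

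**Step 4: column order (constructed example).** If 6 of 7 patients reach target and average 65%, the table prints 65%. The all-patient mean is 6/7 x 65 = 55.7%. A column in which 7 of 7 average 60% prints lower but is truly higher.

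**Step 5: categories.** Eight patients in the top band, with 4 of 20 never at target, is 8/16 = 50% or 8/20 = 40%, depending on the denominator.

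**The case against.** The strongest reply is that the SAP names the subset in the sentence that defines the statistic. The figure is correct for patients who reached target and overstates only if read as an all-patient figure. That is true, but naming the subset does not supply the missing all-patient statistic.

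The measure is also low in the hierarchy. It is not a listed endpoint, nothing is tested, and the by-visit values, changes and percent changes carry no such restriction. This stands and limits the severity.

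Other outputs would show never-reachers: the per-patient figures, the table of maximum percent reduction, and the category table if its lowest band includes them. They help a careful reader, but they do not give the all-patient median or settle the category denominator.

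The size rests on assumptions, and the larger distortions need wide between-patient spread. Protocol 1.1 puts most PH1 patients above 2x ULN, but that describes the disease and does not give p on treatment. The ULN results in Steps 2 and 3 depend on the subset being redefined at ULN; if one population is used for both thresholds, inversion cannot occur. Both points stand.

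Finally, the SAP does not say outright whether the first interval starts at baseline. If it does, a never-reacher whose baseline was at or below the threshold would score above 0. The SAP's denominator refers to post-baseline collections, so the exact zero follows on the natural reading.

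**Conclusion.** The concern holds. An explicit rule selects patients on the outcome being summarised, drops exact zeros, and inflates the mean by 1/p, where p is the share of evaluable patients ever at the threshold. The identity is exact when intervals run between post-baseline collections.

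The size in this trial is unknown. It is nil if every patient reaches 1.5x ULN, 1.25x at 16 of 20, and 2.0x at 10 of 20. At ULN the factor is at least as large if the subset is redefined there. The median can move much further than the mean.

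The primary endpoint and the by-visit oxalate summaries are untouched. The point should be fixed because the bias runs in one direction and the remedy is cheap.

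**What to change.** In SAP 7.2.1:

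1. Compute percentage of time at both thresholds in all evaluable PD Analysis Set patients, counting 0% for those never at the threshold. Define evaluable; at least two valid post-baseline collections is a workable rule, since interpolation needs an interval. Say whether the first interval starts at the first post-baseline collection.
2. State that the category percentages use the same denominator, with never-reachers in the lowest band or in a separate 0% row.
3. Report the number ever at threshold over that denominator, by regimen and in total, for each threshold.
4. Keep the responder-only statistics, if wanted, as a labelled supplement.

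The cost is one programming filter, one stated denominator and one added row, with no new data. The printed time at target stays the same if every patient reaches it and becomes less favourable otherwise.

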4.3. Number of Patients

Up to 20 patients are planned for enrollment in this study.

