The sites of injection may be the abdomen, the upper arms, or thighs. If a local reaction around the injection site occurs, photographs may be obtained.

Patients whose disease progresses to requiring a dialysis regimen will continue on their planned dosing regimen. The ALN-GO1 dose will be administered as soon as feasible following the end of dialysis, eg, within 2 hours of completing the dialysis session. If a patient does not receive a dose of ALN-GO1 within the specified dosing window, the Investigator should contact the Medical Monitor. After such consultation, the dose may be administered or considered missed and not administered.

If a patient misses multiple doses of study drug, the Investigator, in consultation with the Medical Monitor, will discuss whether the patient will be able to continue on the study.

Additional details can be found in the Pharmacy Manual. In addition, instructions and procedures related to administration of ALN-GO1 by a patient or caregiver will be provided in the Patient/Caregiver Storage and Administration Instructions.

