7.2. Pharmacodynamic and Renal Assessments

Urine and blood samples will be collected for assessment of PD parameters (oxalate and glycolate concentrations) at the time points in the Schedule of Assessments ([Table 1](#)). See 24-hour urine collection validity criteria in Section [7.2.1](#).

Patients will have the option to bring the 24-hour urine collections to the clinical study center at specified visits, courier samples to the clinical study center or to the vendor performing analyses, or elect to have the 24-hour urine collected during an inpatient stay at the clinical study center for other assessments.

Additionally, blood samples for measurement of eGFR will be obtained at the time points in the Schedule of Assessments ([Table 1](#)). eGFR (mL/min/1.73m²) will be calculated to assess renal function during the study. The calculation will be based on the Modification of Diet in Renal Disease (MDRD) formula for patients ≥ 18 years of age at Screening and the Schwartz Bedside Formula for patients < 18 years of age at Screening.[Levey 2009; Schwartz 2009]

Blood samples will be collected predose for plasma oxalate assessment in all patients, as specified in the Schedule of Assessments. In patients who have disease has progressed to requiring dialysis, if dialysis session is on same day as scheduled visit, blood samples for assessment of plasma oxalate will be collected pre-dialysis. In addition to plasma oxalate assessment, in patients on dialysis who are not anuric (ie, patients who are able to continue to produce urine ≥ 100 ml per day) 24-hour urinary oxalate excretion will continue to be assessed.

Biologic samples for biomarker research and possible metabolic profiling can be retained on behalf of the Sponsor for a maximum of 15 years following the last patient's last visit in the study.

Details regarding the processing and aliquoting of samples for storage and PD analyses are provided in the Laboratory Manual.

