8.1. Determination of Sample Size

Sample size is not determined through a power calculation but based on the number of patients who complete Study ALN-GO1-001 and are eligible to enroll in this study.

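### SAP 7.2.2 has no rule for eGFR once a patient starts dialysis, so a decline that ends in dialysis would be understated

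*SAP*

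**What the plan says.** **eGFR.** SAP 7.2.2 opens with "Analyses of eGFR and measured creatinine clearance over time will be performed on the Safety Analysis Set". For adults, eGFR "will be calculated from serum creatinine (SCr) based on the Modification of Diet in Renal Disease (MDRD) formula for patients" aged 18 or over; children use the bedside Schwartz formula. The outputs are a shift table to the lowest post-baseline category, by-visit values with absolute and percent change, per-patient and mean plots, and a mixed-model slope if appropriate. No dialysis rule is attached to any of them.

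**Urine measures.** For BSA-corrected 24-hour oxalate, SAP 7.2.1 requires, among other things, "no missing voids and the sample was not collected within 14 days after the most recent dialysis session, if applicable". The creatinine clearance paragraph of SAP 7.2.2 repeats the condition that "the sample was not collected within 14 days after the most recent dialysis session, if applicable". In SAP 7.3.3 the 24-hour oxalate:creatinine ratio is exempt from these validity criteria.

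**Dialysis on study.** Protocol 5.2 excludes chronic dialysis at entry. Protocol 6.2.2 foresees it later: "Patients whose disease progresses to requiring a dialysis regimen will continue on their planned dosing regimen". Protocol 7.2 sets a sampling rule for plasma oxalate: "if dialysis session is on same day as scheduled visit, blood samples for assessment of plasma oxalate will be collected pre-dialysis". Footnote m of Protocol Table 1 sets the same rule for the PD blood sample. Creatinine and eGFR are in the clinical laboratory panel (Protocol Table 3), a separate row of Table 1 with no pre-dialysis condition.

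**The concern.** eGFR change is a secondary endpoint in both documents. Within one SAP section, one creatinine-based measure is protected against dialysis and the other is not, and no reason is given.

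Dialysis removes creatinine. Both eGFR formulas read lower creatinine as better filtration, so values obtained on dialysis mix native function with machine clearance. Protocol 6.2.2 places the dose soon after a session, and the notes to Table 1 ask for assessments before the dose. A creatinine sample between the end of a session and the dose is therefore allowed.

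By-visit means, change scores, plots and the slope would carry these values. The shift table is largely protected, because it keeps the lowest value and SAP 5.6 lets unscheduled visits count in it. It is not fully protected: scheduled visits are six months apart after Month 12, so a patient could start dialysis before any value below 15 is recorded.

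**Working it through.** There is no figure in the plan to reproduce: "Sample size is not determined through a power calculation but based on the number of patients who complete Study ALN-GO1-001". The check uses the SAP's own eGFR formulas.

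**Inputs from the documents**
- MDRD eGFR varies with creatinine to the power −1.154; Schwartz eGFR varies with its inverse (SAP 7.2.2).
- Size: "Up to 20 patients are planned for enrollment in this study" (Protocol 4.3), with results shown by initial regimen (SAP 5.4).

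**Assumptions**
- Fractional creatinine fall due to dialysis, r = 0.3 to 0.7.
- One dialysis patient with a true eGFR of 10 mL/min/1.73 m².
- A dose group of 5 as the small case.

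**Step 1: inflation factor.** MDRD is multiplied by (1 − r)^−1.154 and Schwartz by 1/(1 − r). These ratios do not depend on the creatinine unit.

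| r | MDRD factor | true 10 reported as | Schwartz factor | true 10 reported as |
|---|---|---|---|---|
| 0.3 | 1.51 | 15.1 | 1.43 | 14.3 |
| 0.5 | 2.23 | 22.3 | 2.00 | 20.0 |
| 0.7 | 4.01 | 40.1 | 3.33 | 33.3 |

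A true 10 leaves the <15 category once creatinine falls by about 30% (MDRD) or 33% (Schwartz).

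**Step 2: shift in a visit mean.** Shift = 10 × (factor − 1)/n.
- MDRD, n = 20: +0.25, +0.61, +1.51 for r = 0.3, 0.5, 0.7.
- MDRD, n = 5: +1.02, +2.45, +6.02.
- Schwartz: +0.21 to +1.17 with n = 20, and +0.86 to +4.67 with n = 5.

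**Step 3: would dropping the patient be better?** Assume the other four in a group of 5 average 67.5.
- True mean: (4 × 67.5 + 10)/5 = 56.0.
- As the SAP stands (MDRD): (270 + 15.1)/5 = 57.0, (270 + 22.3)/5 = 58.5, (270 + 40.1)/5 = 62.0. The errors are +1.0 to +6.0.
- Patient dropped: 270/4 = 67.5, an error of +11.5.
- Last pre-dialysis value carried forward: correct if that value was 10, otherwise too high by (value − 10)/5.

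Exclusion alone errs in the same direction, and by more, over the whole assumed range.

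**Step 4: slope.** Take one assumed patient who falls linearly from 60 at baseline to 10 at Month 24, then has dialysis with a true eGFR of 10 to Month 54. Visits are at Months 0, 3, 6, 9 and 12, then every 6 months. A simple least-squares line stands in for this patient's part of the mixed model.
- True values throughout: −11.4 per year.
- As written, MDRD: −9.88, −7.75, −2.42 per year for r = 0.3, 0.5, 0.7.
- As written, Schwartz: −10.12, −8.42, −4.45 per year.
- Month 54 change, MDRD: −44.9, −37.7, −19.9 against a true −50.
- From Month 24 onward, MDRD: +1.45, +3.50, +8.61 per year, while true function is flat.
- Pre-dialysis values only: −25.0 per year. This is a different quantity, the rate of loss up to dialysis. The contamination itself is the gap between −11.4 and the as-written slopes.

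**The case against.** **A reader might infer that the patient with the worst outcome would be reported as improved.** The documents do not support that. The outputs are change from baseline, baseline is the parent-study value (SAP 5.3), and chronic dialysis is excluded at entry. In the assumed patient every full-period slope and every Month 54 change stays negative. Only the comparison with the last pre-dialysis value turns upward.

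**A reader might also infer that the 14-day exclusion should simply be extended to eGFR.** It is a validity criterion for urine collections, and on regular dialysis it would remove nearly every value. Step 3 shows that this flatters by-visit means more than the present text. The objection stands and shapes the fix.

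**Sampling may already be pre-dialysis.** Protocol 8.2.5 lists eGFR among the PD parameters, so footnote m could be read to cover it. But Protocol 7.2 names oxalate and glycolate as the PD parameters and describes the eGFR samples separately without the condition. A pre-dialysis sample would also still reflect clearance by earlier sessions. This reading favours smaller r; it does not close the gap.

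**Placing dialysis starters in <15 is a convention.** Protocol 1.1 links dialysis to end-stage disease, but no passage gives an eGFR threshold. That stands, so the SAP should label it as a rule.

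**Much is visible anyway.** Laboratory listings and per-patient plots are planned, unscheduled values stay out of by-visit tables, the slope is conditional, and nothing is tested formally. This limits the severity.

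**Conclusion.** The gap is real but modest. SAP 7.2.2 leaves eGFR after the start of dialysis undefined, and its formulas would count dialysis clearance as kidney function. The usual result is an understated decline from baseline, with a possible apparent rise from the last pre-dialysis value.

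The direction follows from the formulas. The size rests on the assumed 30–70% creatinine fall and a true eGFR of 10. With 20 patients the effect on a visit mean is small; in a dose group of about 5 it can reach several units. The point does not show that the eGFR endpoint is unsound, and it has no effect if nobody starts dialysis. It is a cheap improvement, best settled before any such patient's data are seen.

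**What to change.** In SAP 7.2.2:

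1. Count any patient who starts dialysis in the <15 category of the worst post-baseline shift table, state this as a rule, and list these patients with the start date.
2. Use only eGFR values before the start of dialysis in the mixed-model slope, and flag on-dialysis values in the per-patient plots.
3. Do not simply drop these patients from by-visit means. Show the number on dialysis at each visit beside the summary. Give the summary twice: without on-dialysis values, and with the last pre-dialysis eGFR carried forward.

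The cost is a few SAP sentences, a data flag and one extra summary. The dialysis dates are already needed for the urine rule. The downsides are that a few measured values leave the slope, and that a carried-forward value will be somewhat high if it was taken well before dialysis began.

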5.3. Baseline Definitions

Baseline will be defined as the derived baseline value in Study ALN-GO1-001 (refer to SAP ALN-GO1-001, Version 2.0; dated August 13, 2018). For data not collected in the parent study (e.g. KDQOL-36, PedsQOL, Renal Ultrasounds), the baseline value will be defined as the latest collection prior to the first dose of lumasiran in this study.

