Measured urine creatinine clearance at each visit per patient will be calculated as:

$$\text{Urine Creatinine concentration (mg/dL)} * 24\text{-hour urine volume (mL)} / \text{plasma creatinine (mg/dL)} * \text{total minutes of collection time} * 1.73 / \text{BSA}$$

where BSA=square root (mean height (cm)*weight (kg)/3600) at that visit.

Tabular summaries will include actual value, change from baseline and percent change from baseline at each scheduled visit.

Per-patient figures and mean ($+\text{-SEM}$) plots over time of the actual values, change from baseline and percent change from baseline will be generated.

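### SAP 7.2.2 gives creatinine the wrong unit in both eGFR formulas and leaves the measured creatinine clearance denominator unbracketed

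*SAP*

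**What the plan says.** SAP 7.2.2 gives three formulas.

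- **MDRD (adults):** the creatinine term is "175 \times (\text{SCr } [\mu\text{mol/dL}] / 88.4", raised to the power -1.154, with factors for age, sex and race.
- **Bedside Schwartz (under 18):** "36.2 \times \text{height [cm]}) / \text{Scr} (\mu\text{mol /dL".
- **Measured creatinine clearance (mCrCl):** urine creatinine times urine volume, a slash, then "plasma creatinine (mg/dL)} * \text{total minutes of collection time} * 1.73 / \text{BSA". No bracket shows where the denominator ends.

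eGFR is sorted into five categories from ≥90 down to <15 and reported in "A shift table of baseline to worst post-baseline eGFR". It is also summarised as actual value, change and percent change by visit, and a mixed-model slope is planned if appropriate. mCrCl is summarised by visit in the same three ways, using collections of 18 to 26 hours only.

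eGFR is a secondary endpoint in Protocol 3.2 and SAP 3.2.2. mCrCl is secondary in SAP 3.2.2 only. For both, SAP 5.3 applies: "Baseline will be defined as the derived baseline value in Study ALN-GO1-001". Nothing elsewhere in either document corrects these formulas.

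**The concern.** The divisor 88.4 belongs with creatinine in µmol/L, not µmol/dL. A programmer who converts creatinine to the printed unit before applying the formulas would inflate every eGFR. Actual values, absolute changes, the slope and the category shift table would then be wrong. Percent change would survive only if baseline had been computed the same way, and baseline comes from a parent-study derivation that these documents do not show.

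The mCrCl expression has two literal readings, and neither is a BSA-normalised clearance. One multiplies by collection time instead of dividing. The other inverts the BSA correction. Collection time varies between visits and BSA changes as children grow, so neither error cancels in change or percent change.

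**Working it through.** **Inputs.** The formulas, the eGFR categories and the 18 to 26 hour window are from SAP 7.2.2. The one outside constant, stated as an assumption, is the molar mass of creatinine, 113.12 g/mol. Patient values below are illustrative. The plan gives no worked eGFR or mCrCl value to reproduce.

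**1. Unit check**

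- 1 mg/dL = 10,000/113.12 = 88.4 µmol/L = 8.84 µmol/dL. Dividing by 88.4 therefore turns µmol/L into mg/dL.
- The Schwartz evidence is less direct. On the µmol/L scale the constant equals 36.2/88.4 = 0.41 per mg/dL; on the µmol/dL scale it would be 36.2/8.84 = 4.1. The results below show which scale gives usable values.

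**2. Size if creatinine is entered in µmol/dL**

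| | MDRD | Schwartz |
|---|---|---|
| Inflation | 10^1.154 = 14.26 | 10 |
| Example | man aged 30, 88.4 µmol/L: 175 × 1 × 30^-0.203 = 87.7 | 140 cm, 70 µmol/L: 36.2 × 140/70 = 72.4 |
| Same patient, printed unit | 1251 | 724 |
| Lowest true eGFR classed ≥90 | 90/14.26 = 6.3 | 90/10 = 9.0 |
| True eGFR must be below this to be classed <15 | 15/14.26 = 1.05 | 15/10 = 1.5 |

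Protocol 5.2 excludes patients who need chronic dialysis at entry, so nearly every value would fall in one category.

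If the parent-study baseline used µmol/L and this study used the printed unit, an unchanged eGFR would show as 14.26 - 1 = +1326% (MDRD) or 10 - 1 = +900% (Schwartz). This is conditional on a derivation not shown here.

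**3. mCrCl**

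Let U and P be urine and plasma creatinine (mg/dL), V the volume (mL) and T the collection time (minutes).

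- Correct form: [U × V]/[P × T] × 1.73/BSA, in mL/min per 1.73 m².
- Reading A, ordinary precedence: (U × V/P) × T × 1.73/BSA. Before BSA scaling the unit is mL·min. Ratio to correct: T².
- Reading B, everything after the first slash in the denominator: U × V/(P × T × 1.73/BSA). Ratio to correct: (BSA/1.73)².

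Illustration with U = 60, V = 2000, P = 1.0, T = 1440, 165 cm and 60 kg (BSA 1.658 m²):

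- Correct: 86.9.
- Reading A: 180,270,015 (T² = 2,073,600).
- Reading B: 79.9.

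Reading A, apparent change when true clearance is constant:

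- 23.5 h then 24.5 h: (24.5/23.5)² = 1.087, or +8.7%.
- 18 h then 26 h: (26/18)² = 2.086, or +109%.
- 26 h then 18 h: (18/26)² = 0.479, or -52%.

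Reading B, error factor (BSA/1.73)²: 0.33 at 1.0 m², 0.75 at 1.5 m² and 1.34 at 2.0 m². A child growing from 1.0 to 1.3 m² with constant true normalised clearance would show (1.3/1.0)² = 1.69, or +69%.

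**The case against.** The strongest reply is that these are typographical slips with little practical risk. A wrong unit label does not convert any data. Both eGFR equations are named, SAP 7.3.1 has laboratory parameters in SI units, and a programmer working from µmol/L data would get correct eGFR without noticing the label. An eGFR of 1251 or a clearance of 180 million would not reach a table. All the outputs are descriptive, in at most 20 patients. The mixed-baseline percentages need two different derivations, for which there is no evidence. The mCrCl bracket may also have been lost when the PDF was read.

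Much of this stands. Literal eGFR coding and reading A of mCrCl would probably be caught, and the mixed-baseline figures and the 18 to 26 hour extremes are limits, not expectations. But the SI statement does not name a creatinine unit or amend the formulas, and these formulas are what the programming is checked against. Reading B is not self-revealing: 79.9 in place of 86.9 looks ordinary, and its error drifts with a child's growth. Loss of the bracket in PDF reading cannot be ruled out, although the oxalate formula in SAP 7.2.1 kept its brackets, including those around "24 hours/actual collection hours". The unit error does not depend on any bracket.

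**Conclusion.** The concern holds and should be fixed. As printed, the eGFR formulas overstate by 14.3 times (MDRD) and 10 times (Schwartz), given the assumed molar mass. The mCrCl formula, as it reads in the supplied text, is wrong by T² or by (BSA/1.73)², depending on how it is parsed. Confidence is high on the eGFR unit. On mCrCl it is subject to a check of the source PDF. The consequences are confined to secondary endpoints and arise only if the printed text is followed; the primary endpoint, incidence of adverse events, is unaffected.

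**What to change.** Three formulas in SAP 7.2.2 need editing:

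1. MDRD: change the creatinine unit to µmol/L.
2. Bedside Schwartz: change the creatinine unit to µmol/L.
3. mCrCl: write [urine creatinine (mg/dL) × urine volume (mL)] / [plasma creatinine (mg/dL) × collection minutes] × 1.73/BSA, after checking the source PDF for a bracket.

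Confirm at the same time that the parent-study eGFR baseline was derived with the same formula and unit. While the MDRD line is open, also clarify how the sex and race factors combine, since they are joined by an or and a patient meeting both conditions is left undefined.

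The cost is a SAP text correction and a check of the programs against it. No new data and no protocol amendment are needed.
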